The proposed project will evaluate the effectiveness of three different implementation strategies for integrating MI into the YNHH's internal medicine hospitalist service and other general medical inpatient units. Specifically, we will randomize 30 Healthcare providers to one of three conditions: (1) a continuing medical education workshop that "shows" the healthcare providers MI (the control condition, referred to as SEE ONE); (2) a 'see one, do one' apprenticeship model involving workshop training plus live supervision of bedside practice (DO ONE); and (3) ordering MI from CL after learning about it in a workshop (ORDER ONE). After receiving the respective MI training, each Healthcare provider will be followed for provision of MI to study-eligible/consented patients. In ORDER ONE, healthcare providers may elect to conduct MI themselves or order it to be conducted by Psychiatrists from the CL service.

After the Healthcare providers have attended their respective workshops, research staff will identify substance using patients in need of a MI intervention. Research staff will independently screen, assess and obtain consent from eligible patients who are admitted to the internal medicine hospitalist service and other general medical inpatient units. Patients will be potentially included if they are assigned to a participating Healthcare provider according to the hospital's usual clinical administrative procedures. Thus, patients will follow the randomization condition of their Healthcare provider, though Healthcare provider will not know which patients on their caseloads have enrolled in the study. This approach will permit a naturalistic test of the Healthcare provider's ability to identify and intervene using MI with patients who have substance use problems. Each Healthcare provider will be followed until he or she has

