Primary outcomes will be 1) the percentage of MI sessions, as verified by audio recordings, conducted among each Healthcare provider 40 consecutively enrolled study patients, 2) independently rated MI adherence and competence ratings of the sessions, and 3) the percentage of sessions conducted that meet a criterion level of adequate MI performance used in MI effectiveness¹⁸⁻²⁰ and clinician training trials.^{21,22} In addition, we will calculate the relative costs and cost effectiveness of the three conditions. Secondary outcomes will be 1) independently rated strength and frequency of patient statements that favor change in the sessions (called change talk) as a proxy for patient outcomes,^{23,24} and 2) themes related to implementation facilitators and barriers identified through qualitative interviews. The YNHH hospitalist and the psychiatric CL services will work closely with research staff to implement all aspects of this project.

Initially our main unit of randomization was the PAs within the YNHH hospitalist service. The director of the hospitalist service, [name], and [name], Chief PA of the hospitalist service, both co-investigators on this proposal, have committed the participation of the PAs on the service to the protocol. The service includes 33 PAs who work during days Mon-Fri on non-critical care general medical units. There is a turnover rate of about 2 per year that nets 40 PAs during the 4-year data collection phase of the project. Prior to randomization, [name], [name] and other members of the study team will meet with the PAs during staff meetings, wherein we will describe the project and elicit interest. Thereafter, we will screen PAs for eligibility and obtain written consent for their participation. PAs will next complete baseline assessment, including an audio recorded sample of their usual manner of interviewing an inpatient with a substance use problem. Following baseline assessments, a restricted randomization procedure will be used to allocate an equal number of PAs to the three conditions (10 PAs per condition).

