- **Independent Tape Rater Scale (ITRS)** will assess the integrity of MI delivery and the criterion level of adequate MI performance within each session collected at baseline and during the trial. The ITRS includes items that cover therapeutic strategies that are MI consistent (e.g. reflections) or inconsistent (e.g., unsolicited advice). It also has items detailing general counseling strategies (e.g., assessment of substance use) that are not unique to MI, nor antithetical to it, and interventions particular to other substance abuse treatment approaches (e.g., coping skill development). For each item, raters evaluate the practitioners for adherence (i.e., the extent of intervention delivery) and competence (i.e., the skill/quality of intervention delivery) along 7-

point Likert scales. For our primary outcomes, we will: 1) calculate mean adherence and competence scores for the two factors (fundamental and advanced MI strategies) identified in prior psychometric analyses;⁹¹⁻⁹³ and 2) determine if sessions achieve our criterion level for adequately performing MI,¹⁸⁻²² namely, at least half the MI consistent items rated average or above for both adherence and competence. Descriptive analysis of other specific and general substance abuse interventions that do not involve MI will permit identification of how Healthcare providers and Psychiatrists from CL deviate from or modify the MI intervention for the inpatient setting, an important issue when studying the implementation of evidence-based treatments in real world settings.^{125,126} We have extensive experience training ITRS raters to perform very reliable MI session process ratings.^{21,22,91,93}

4. Results level (results that occurred from the application of the new practice)

- **Motivational Interviewing Skills Code 2.1 Client Language Coding System**¹³⁰ will obtain frequency counts and strength indices of positive (change talk) and negative (sustain talk) language categories in four categories: reason (includes desire, ability, and need statements as subcategories), other (hypothetical advice to others, if-then statements about the possibility of changing, foretelling of future problems if change does not occur, problem recognition), taking steps, and commitment.

5. Healthcare provider, patient, and work environment characteristics

- **Clinician Survey**¹²⁷ collects baseline Healthcare provider demographics and background.

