The potential risks in this study are related to psychiatric interviewing and loss of confidentiality for medical inpatients and for Healthcare provider participants.

10. Minimizing Risks: Describe the manner in which the above-mentioned risks will be minimized.

For the Healthcare provider participants, a Research Assistant, Project Director, or Investigator will obtain written consent from Healthcare providers. Medical information will not be collected from Healthcare providers but we will collect information on attitudes, experience and demographic background. This will all be coded under a subject ID and kept on password protected data bases and in double locked files in the offices of research staff. Any information that is collected from subjects who are not eligible to participate (including screening information from those who have not provided consent or audiotapes from those who have not consented to participate in the study), will be destroyed.

For potentially eligible medical inpatients, information will be kept in a research chart that is not available to non-research staff unless safety issues mandate disclosure (e.g., risk of self harm or harm to others). In this case, the subject will be apprised of safety concerns and the need to inform his or her primary clinician about psychiatric or behavioral health concerns. Only the minimal necessary information will be disclosed. We have obtained a Certificate of Confidentiality that will facilitate frank sharing of information between the researchers and the patients. However, the patient subjects will also be apprised of the limitations of the certificate which, as above, include risk of self harm or harm to others.

11. Data and Safety Monitoring Plan: Include an appropriate Data and Safety Monitoring Plan (DSMP) based on the investigator's risk assessment stated below. (Note: the HIC will make the final determination of the risk to subjects.) For more information, see the Instructions, page 24.

- a. What is the investigator's assessment of the overall risk level for subjects participating in this study? Minimal
- b. If children are involved, what is the investigator's assessment of the overall risk level for the children participating in this study? N/A
- c. Copy, paste, and then tailor an appropriate Data and Safety Monitoring Plan from <http://www.yale.edu/hrpp/forms-templates/biomedical.html> for
 - i. Minimal risk
 - ii. Greater than minimal/moderate risk
 - iii. High risk

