Procedures for highly efficient, real-time managing, monitoring, and analysis of data have been developed and refined by our research group. We are using OnCore, Yale's new Clinical Trials Management System (CTMS), to track procedures and data entry for patient characteristics and outcomes. Participants enter data directly into the computer via CASI. All computers are encrypted and password protected. Identifying data are not kept on the computer. For office PCs where data that were collected on paper is entered, we use a double entry method (staff data) and regular data checks to assess the integrity of the data base and missing data. After data entry and cleaning, de-identified data are moved to SAS databases for analysis.

2. Data analysis for quantitative primary and secondary outcomes

Outlined below is the general strategy for data analyses which will address each of our specific aims: (1) assess the uptake of MI by Healthcare providers on the medical units; (2) assess the integrity of MI when Healthcare providers use it on the medical units; (3) assess the cost-effectiveness of the three strategies; (4) determine how long the initial training effects endure across the study period.

- *Data reduction:* Primary outcome variables have been defined *a priori* to reduce the risk of Type I error. Preparatory analyses will include evaluation of baseline equivalence of groups on demographic and comparability of rates of data availability across conditions. If imbalances exist we will enter the unbalanced variables as covariates in the models below. Descriptive statistics for all outcome variables will be calculated prior to statistical analysis. Continuous outcome

variables will be evaluated for normality and transformations will be applied as necessary. Two-sided tests and overall alpha level of 0.05 for all primary hypotheses will be used.

- *Strategies for management of differential attrition:* We do not expect differential attrition across conditions in that the rate of Healthcare provider job turnover is very low and their activities in the study overlap considerably with their normal duties. However, in the event of Healthcare provider discontinuation in the trial, we will recruit new Healthcare provider hires to maintain a balanced design.

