- *Evaluation of effects at implementation strategies:* The principal strategy for assessing the effectiveness of the study implementation conditions on outcome will be mixed effects general linear models for continuously measured primary (e.g., MI integrity) and secondary (e.g., strength and frequency of patient change talk) outcomes variables, and generalized linear mixed models for binary outcomes (e.g. meets criterion MI performance threshold). In both types of models we will have training condition as the main predictor variable and will include random effects for Healthcare providers to account for clustering of observations within Healthcare providers. Our main hypotheses involve group comparisons with the SEE IT group as the reference condition. We will consider significant comparisons of the DO IT and ORDER IT conditions to the SEE IT condition as supportive of our hypotheses. Comparisons of DO IT with ORDER IT will be conducted for exploratory purposes only.

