- *Adequacy of sample size for primary hypotheses:* Effect sizes for power estimation for the continuous outcomes were based on studies by Miller et al.²³ (d=0.4 to 0.8) and [name] et al.²¹ (d=0.4 to 1.2). A review article by Apodaca and Longabaugh¹⁴⁸ also suggests that at least medium effect sizes are expected for the between-group comparisons. [name] et al.²¹ observed large effect sizes for the binary outcome comparison (meets criterion MI performance threshold, 53% vs. 18%); however, we conservatively assume a medium effect size for this comparison as well. Intra-class correlations accounting for expected within clinician variance were estimated based on Imel et al¹⁴⁹ and are expected to be small (in the 0.05 to 0.10 range). Feasibility constraints (i.e., 10 Healthcare providers per condition) limited the number of clusters (Healthcare providers) that we could consider. Finally, because we do not expect all Healthcare providers to identify substance using patients and use MI with them (i.e., our 1st hypothesis about MI uptake), we will require a larger sample size of study-enrolled patients to reach our targeted number of audio recorded MI sessions for hypothesis testing purposes. We estimate 80% of patients across conditions will receive MI. Based on these estimates and constraints, alpha level of 0.05 and power of 80%, 30 Healthcare providers and 40 patients per Healthcare provider will be sufficient for testing the primary hypotheses of the study. Table 2 shows the actual total sample size for the cluster-randomized design for continuous and binary outcomes, adjusted for a conservative estimate of MI uptake.

Table 2: Sample size estimates for the primary aims of the study based on alpha=0.05 for the pairwise comparisons of each condition to the control condition and 80% power.

Effect size	Total sample size for an ordinary RCT (3 arms)	ICC	Number of Healthcare provider	Average number of patients per Healthcare provider	Total sample size for a cluster RCT unadjusted for estimated MI uptake	Total sample size for a cluster RCT adjusted for estimated MI uptake
d=0.4	300	0.07	31	31	930	1116
40% vs 18%	195	0.1	30	17	510	765

3. Incremental cost-effectiveness analyses

The relative cost-effectiveness of the three MI implementation strategies will be assessed using both incremental cost-effectiveness ratios (ICERs) and cost-effectiveness acceptability curves (CEACs).

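### Baseline ITRS proficiency is collected before randomisation but is not a prespecified covariate in the H2 models; adding it gives a modest gain, and the recording-retention wording should be reconciled with it.

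*Combined protocol and SAP*

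**What the plan says.** **Baseline measurement.** Section V, item 3 (Research Plan) places this step before randomisation: "PAs will next complete baseline assessment, including an audio recorded sample of their usual manner of interviewing an inpatient with a substance use problem". The sentence is written for PAs, but Table 1 marks the ITRS at baseline for healthcare providers generally. The ITRS entry under Assessments (H.3, Behavior level) says the scale is applied "within each session collected at baseline and during the trial". The same scale supplies the H2 primary outcomes: mean adherence and competence on two factors, and the criterion of adequate performance.

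**Models.** Section V, item 12, Evaluation of effects: "In both types of models we will have training condition as the main predictor variable and will include random effects for Healthcare providers". No baseline term is named.

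**Covariate rule.** Item 12, Data reduction, adds covariates only where groups are found to be unbalanced. The check it describes covers demographics and rates of data availability.

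**Recordings.** Item 10 (Minimizing Risks) says that information from ineligible people, including "audiotapes from those who have not consented to participate in the study), will be destroyed". Part G of the Research Plan, the audio-recording paragraph of Section VII item 9, and Section VIII item b erase, or do not retain, recordings of people who are not study patients. Patient identification comes later: "After the Healthcare providers have attended their respective workshops, research staff will identify substance using patients in need of a MI intervention".

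**The concern.** The number of providers is fixed by feasibility at 10 per condition. At the plan's ICCs, differences between providers account for most of the variance of an arm mean, and more patients per provider cannot reduce that part. A provider-level baseline on the outcome scale acts on it directly, and the trial already collects one. Leaving it out forgoes some precision and leaves chance differences in starting skill between two groups of 10 uncorrected.

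The conditional rule is a poor substitute. It does not clearly reach baseline ITRS. It also gives no threshold for imbalance, so the model would be chosen after seeing the data. That sits badly with the same paragraph's aim of defining matters in advance to limit Type I error.

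There is also a practical dependency: the covariate is usable only if the baseline recording survives until it is rated.

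**Working it through.** **Inputs from the plan**
- Alpha and power: "alpha level of 0.05 and power of 80" per cent, two-sided. The table caption says "Sample size estimates for the primary aims of the study based on alpha=0.05 for the pairwise comparisons of each condition to the control condition", so 0.05 is used per contrast here. Data reduction instead has "Two-sided tests and overall alpha level of 0.05 for all primary hypotheses will be used"; a split alpha would lower the power both with and without the covariate.
- d = 0.4 with SD 1; ICC 0.05 to 0.10 (0.07 in the d = 0.4 row of Table 2).
- k = 10 providers per arm; 40 patients each at 80% uptake gives m = 0.80 × 40 = 32 sessions.
- One recorded baseline sample per provider.

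**Reproducing Table 2.** Two means at d = 0.4 need 99 per arm, or 297 for three arms (printed 300). The design effect is 1 + (31 − 1) × 0.07 = 3.10, and 300 × 3.10 = 930, as printed. This corresponds to 30 providers of 31 patients; the printed 31 providers would give 961.

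**Variance without the covariate.** Var(difference) = (2/k) × [ICC + (1 − ICC)/m]. At ICC 0.07 the bracket is 0.0700 + 0.93/32 = 0.0991. The between-provider share is 0.05/0.0797 = 63%, 0.07/0.0991 = 71% and 0.10/0.1281 = 78% at ICC 0.05, 0.07 and 0.10.

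**How much one session can explain.** The documents give no baseline-to-outcome correlation. Assumption: the baseline session has the same ICC as trial sessions. Its squared correlation with the later provider effect is then R² = ICC × s², where s is the correlation between a provider's true skill before and after training. The ceiling, at s = 1, is R² = ICC. At ICC 0.07 this caps the correlation at √0.07 ≈ 0.26.

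**Variance with the covariate.** The bracket becomes ICC(1 − R²) + (1 − ICC)/m. At the ceiling:

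| ICC | Bracket before | Bracket after | Variance cut | Power, normal | Power, t (27 to 26 df) |
|---|---|---|---|---|---|
| 0.05 | 0.0797 | 0.0772 | 3.1% | 88.7% to 89.6% | 86.3% to 87.3% |
| 0.07 | 0.0991 | 0.0942 | 4.9% | 81.1% to 83.0% | 78.2% to 80.1% |
| 0.10 | 0.1281 | 0.1181 | 7.8% | 70.5% to 74.0% | 67.3% to 70.7% |

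Check at ICC 0.07: SE = √(0.2 × 0.0991) = 0.1408; 0.4/0.1408 − 1.96 = 0.88, which gives 81.1%.

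**Sensitivity**
- With s = 0.7 the cut is 1.5% to 3.8%; with s = 0.5 it is 0.8% to 2.0%.
- With 40 sessions instead of 32, the ceiling at ICC 0.07 is 5.3%.
- Criterion outcome (m = 17, ICC 0.10, linear approximation): 0.01/(0.10 + 0.90/17) = 6.5% at best.
- H2b, if the covariate carries no information in ORDER ONE: only one arm benefits, so the ceilings halve to about 1.6%, 2.5% and 3.9%.

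**Chance imbalance.** The SD of the difference in mean true skill between two arms of 10 is √(2 × ICC/10): 0.12 at ICC 0.07 and 0.14 at 0.10, or 30% to 35% of d = 0.4. One noisy session corrects only part of this; that part is the variance cut above.

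**The case against.** The strongest objection is that the gain is too small to matter. On the plan's own ICC that is largely right: at most 1 to 3.5 power points, and less with imperfect stability or for H2b. What remains is that the measurement is already paid for and that naming the covariate in advance removes a data-driven choice.

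A reader might infer a much larger benefit, or that this is the best precision gain open to the trial. If baseline explained 20% to 30% of between-provider variance, the contrast variance would fall 14% to 21% at ICC 0.07 and power would reach 87% to 89%. The documents do not support that. One session at ICC 0.05 to 0.10 can explain at most 5% to 10%. A larger gain needs a more reliable baseline or a higher ICC; at ICC 0.30, for example, the ceiling is a 28% cut, but power only goes from 35% to 46%. No other covariate has been compared. Recruitment beyond PAs may widen the spread of skill, but no figure is given.

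A reader might also infer that the recording rules require the baseline tape to be destroyed. That is too strong. Part G and the Section VII and VIII passages are written about MI sessions, whereas the baseline sample is usual interviewing. The item 10 clause stands in a paragraph about provider participants. The ITRS entry plainly intends baseline sessions to be rated. Section VII item 11 says authorisation forms are attached; they were not available for this check and may contain a consent route. What stands is a wording conflict: no patient is yet enrolled when the baseline tape is made, and the text seen here gives no exception for it.

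**Conclusion.** The omission is real: an outcome baseline measured before randomisation has no prespecified place in the H2 models, and the conditional covariate rule does not clearly supply one. Its size is modest, at most a 3% to 8% cut in contrast variance across the plan's ICC range. This rests on one baseline session with the same ICC as trial sessions, perfect stability of skill, 32 sessions per provider and alpha 0.05 per contrast. Weaker stability lowers the gain, as does delivery by CL psychiatrists in ORDER ONE. The case for the change is good practice at almost no cost, with partial protection against chance imbalance among 10 clusters per arm; it does not rescue power. The recording point is secondary and calls for clarification.

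**What to change.** 1. In Section V, item 12, Evaluation of effects, add the provider's centred baseline ITRS score as a fixed covariate in the H2 models, regardless of observed imbalance. Match it to the outcome by factor and by adherence or competence. For the criterion model, name the baseline score in advance. A continuous score may serve better than baseline criterion status, which could hardly vary because providers already formally supervised in MI on the units are excluded (an inference).
2. State that the covariate is less informative in ORDER ONE, and whether that arm gets its own slope.
3. Say how a provider without a usable baseline tape is handled, so that no provider drops out of the model.
4. Reconcile Part G, item 10, Section VII item 9 and Section VIII item b with the planned baseline rating. One sentence should state under what patient permission the baseline recording is made and that it is kept at least until rated.

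Cost: 1 degree of freedom for a common slope, 2 with a separate ORDER ONE slope, and a few sentences of text. No new measurement is needed.
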